This study focuses specifically on smoking cessation in young adults (ages 18 to 20) because prior research indicates this age group is particularly vulnerable to nicotine dependence and the harmful effects of tobacco. Thus, we will only recruit participants aged 18 to 29 years old and will exclude children under the age of 18.

For protocols including the use of an investigational drug, indicate whether women of childbearing potential have been included and, if not, include appropriate justification.

If a participant is female, she will be excluded if she is pregnant, planning to become pregnant in the next 3 months, or of reproductive potential, sexually active with a male partner and not using protection or on birth control.

If HIV testing is included specifically for research purposes explain how the test results will be protected against unauthorized disclosure. Include if the subjects are to be informed of the test results. If yes, include the process and provision for counseling. If no, a rationale for not informing the subjects should be included.

Not applicable

Will the SONA psychology Pool be utilized? Include documentation indicating permission to use this recruiting tool

Yes

No

FINANCIAL CONSIDERATIONS

Describe all potential research related expenses to subjects:

N/A

Compensation for participation: Describe all plans to pay subjects, either in cash, a gift or gift certificate. Please note that all payments must be prorated throughout the life of the study. The IRB will not approve a study where there is only a lump sum payment at the end of the study because this can be considered coercive. The amount of payment must be justified. Clarify if subjects will be reimbursed for travel or other expenses.

Not applicable

All participants will have the opportunity to earn up to \$493 in online gift cards for participating in this 6-month study. Links to digital gift cards will primarily be sent via Rybbon, a vendor that we work with to deliver gift cards. Depending on availability, we may also send participants Amazon.com digital gift cards directly from our study email account ([contact]). The table below outlines compensation for each study activity:

Study activity	Compensation
Initial call & ID verification	\$15 total
Baseline survey	\$35 total
Viewing short informational video	\$10 total
2 weeks of daily daily questionnaires	\$2 per log entry for a total of \$28
Week 1 + 2 surveys (\$10 each)	\$20 total
Week 3 + 4 surveys (\$15 each)	\$30 total

Week 5 + 6 surveys (\$20 each)	\$40 total
Week 7 + 8 surveys (\$25 each)	\$50 total
Week 9 + 10 surveys (\$30 each)	\$60 total
Week 11 survey (\$35)	\$35 total
3 month and 6 month surveys	\$50 each for a total of \$100
Bonus for providing breath samples on baseline, weekly surveys, and 3-month and 6-month follow-up surveys	\$5 per bonus for a total of \$70
Total possible compensation	\$493

Collaborating Institutions

Will this research be conducted in collaboration with other sites at other locations?

Yes No

If so, complete the following for all collaborating institutions:

Institution Name	Describe Involvement	Is there an IRB? If yes, attach approval or explanation	Are other permissions required? If yes, attach approval or explanation

INFORMED CONSENT**a. Type of Consent**

i. Are you obtaining Written Consent?

	Yes		No
	Yes		No

If yes, will there be more than one consent document?

If yes, how many consent documents and for what populations.

Potential participants will review an electronic consent form via REDCap. Potential participants will be provided with a study phone number and e-mail and encouraged to contact study personnel if they have any questions about the study or consent form. After reviewing, the potential participant will be asked to provide an electronic consent by using REDCap's e-consent program. After the electronic consent, participants will complete the electronic consent survey, which evaluates their understanding of the information from the consent form. This survey will provide immediate, correct responses for any items answered incorrectly. We will also include consent process documentation.

ii. Are you requesting a Waiver of Informed Consent?

	Yes		No
--------------------------	-----	-------------------------------------	----

This request means that you will not be obtaining verbal nor written consent. If yes, complete the form Request for a Waiver of Informed Consent/Authorization/Documentation in UVMClick.

iii. Are you requesting an Alteration of Informed Consent Procedures?

	Yes		No
--------------------------	-----	-------------------------------------	----

This is a request to alter an individual's informed consent or elements of informed consent. Deception in research would be one example when consent would be altered. See [Policies and Procedures Manual](#) for more information about when a subject's consent may be altered. If yes, complete the smart form Request for a Waiver of Informed Consent/ Authorization/ Documentation in UVMClick.

iv. Are you requesting a Waiver of Documentation of Informed Consent?

	Yes		No
--------------------------	-----	-------------------------------------	----

This request means you are obtaining verbal or implied consent without obtaining the subject's signature on a consent form. See manual for the criteria required to obtain this type of waiver.

If yes, complete the form Request for a Waiver of Informed Consent/Authorization/Documentation in UVMClick.

v. Do you intend to obtain consent from a legally authorized representative?

	Yes		No
--------------------------	-----	-------------------------------------	----

If **yes**, describe the process.

vi. Are you requesting a short form consent process for non-English speaking subjects? Yes No
If yes, please describe. Guidance available in the [Policies and Procedures Manual](#).

b. Consent Process

i. Once a prospective subject is identified, who initiates the informed consent discussion and answers questions presented by the subject or the subject's family?

The informed consent process will be initiated electronically. People who are interested in participating will be directed to a website with information regarding the study. Potential participants will be provided with a study phone number and e-mail and encouraged to contact IRB-approved research personnel if they have any questions about the study or consent form.

ii. Where (in what setting) is the informed consent process initiated? How much time is the subject given to decide?

Consent will be obtained remotely using e-consent procedures through REDCap. Participants will have as long as they need to review the consent form and ask questions.

iii. Is the principal investigator present for the initial and subsequent informed consent discussions with the subject?

The PI will not be present at the time of consent although his contact information is available on the consent form for questions and the research assistant will have him speak with the potential participant prior to consent as needed.

iv. What other method of documentation is used to record the informed consent process, in addition to the executed consent form? See an [example of documentation](#) of the informed consent **process** under consent templates on our forms page. (*This separate documentation is required to document the consent process with the research subject*)

We are using a consent survey to document understanding of key procedures from the consent form. We will also include consent process documentation.

Information Withheld From Subjects: Will any information about the research purpose and design be withheld from potential or participating subjects? If so, explain and justify the non-disclosure and describe plans for post-study debriefing.

Not applicable

Research Data Management Plan: The Research Data Management and Security Plan form must be completed. The form, along with guidance, can be found in our [forms library](#) and must be submitted with your initial application.

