Adverse events will be assessed weekly throughout the 12-week treatment period, at the end of treatment follow-up, and at the 6-month follow-up. Participants who report they have experienced one or more problems related to their study participation will be prompted to rate the severity of their problem. Research personnel will contact all participants who report one or more severe problems related to study participation to further evaluate the nature of the adverse event(s). Research personnel will then consult with the study licensed medical provider to determine whether further evaluation is needed, whether the participant should be withdrawn from the study, or whether the participant should be referred to their local hospital. Any FDA-defined "serious" and possibly-related AEs will be reported within 72 hours to our IRB and our data and safety monitoring and review board (DSMB). In addition, all participants will be provided with a study telephone number and email at the outset of the study and instructed to contact research personnel with questions about symptoms or study procedures. It is possible that some participants in conditions A and C will increase their EC use when quitting CCs. An increase in EC use among those who completely quit CCs will not be considered an adverse event because completely switching from CCs to ECs is likely to result in substantial harm reduction.^{82,135-139} In contrast, self-reported increases in EC use of > 100% among participants who continue to smoke CCs will be considered an adverse event. Research personnel will call any participant who continues to smoke CCs and reports an increase in EC use from baseline of >100% for one week (i.e., 7 consecutive days) or more and encourage them to reduce their EC use or quit CCs. Any participant who continues to smoke CCs and use > 100% of baseline ECs for two consecutive weeks will be referred to the national quitline and removed from this study.

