Treatment. The consent form explains that a primary aim of this RCT is to test whether quitting versus continuing ECs is more effective when quitting CCs, and currently there is mixed evidence supporting both strategies. After randomization, all participants will receive information about the study including instructions to set a quit date and which product(s) to quit. Written instructions for the intervention will be provided and participants will also be asked to view a supplementary video presentation. We will provide participants in groups A and C with instructions to quit CCs but continue using ECs with the rationale that ongoing use of ECs could help them abstain from CCs. Specifically, we will instruct participants in groups A and C to use ECs in place of CCs to help cope with cravings or urges to smoke CCs. In contrast, participants randomized to conditions B and D will receive instructions to quit CCs and quit ECs with the rationale that quitting ECs could help them abstain from CCs. We will instruct participants in groups B and D to abstain from vaping because ECs could trigger relapse to CCs. Participants in groups A and B will also receive instructions for how to use NRT.

Participants randomized to conditions A and B will be mailed 3 one-month supplies of dual 14 mg NRT patches and 4 mg mini-lozenge because this appears to be the most effective non-prescription medication combination for smoking cessation.¹⁴⁰ However, participants will have the option to stop receiving NRT from the study. Participants will be instructed to start using both forms of NRT 2 weeks prior to their quit date because pre-quit NRT appears to increase the effectiveness of NRT.¹⁴¹ Further, the recommended use for the NRT has recently been changed to incorporate use while smoking because "the FDA has determined that there are no significant concerns with using NRT products at the same time as another nicotine-containing product like a cigarette (<https://www.nicodermcq.com/faq.html>)."¹⁴² We will instruct participants to use one patch per day and use mini-lozenges when they have cravings to smoke CCs (condition A) or cravings to smoke CCs or use ECs (condition B), without surpassing 24 mini-lozenges in one 24-hour period. Anyone for whom NRT is contraindicated will be excluded from the proposed RCT. In addition, though risk of serious adverse events from NRT is low (eg.¹⁴²), we will assess adverse events related to study procedures on weekly surveys.

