Statistical methods. Baseline participant characteristics, including socio-demographic information and tobacco use history, will be compared between the four conditions using analyses of variance for continuous and chi-square tests for categorical variables. Differences between conditions at baseline will be considered as potential covariates in subsequent analyses. Consistent with the intent-to-treat approach,¹⁵² our primary analysis will include all randomized participants who complete the baseline survey, independent of early dropout. Participants who are missing abstinence data will be assumed to be smoking. Missing survey data on other outcomes will be imputed using multiple imputation.¹⁵³ For our Aim 1 primary outcome, we will compare the proportion of participants who achieved CO-verified (< 6 ppm) 7-day point-prevalence abstinence at the end of treatment between conditions that were provided NRT versus no NRT using logistic regression. For our Aim 2 primary outcome we will compare the proportion of participants who achieved CO-verified 7-day point-prevalence abstinence at the end of treatment between conditions assigned to quit CCs only versus quit CCs and Ecs simultaneously. For our Aim 3 primary outcome we will compare the conditions assigned to quit CCs only versus quit CCs and Ecs simultaneously on 1) the proportion of participants who report a serious study-related adverse event using a chi-square test and 2) the total number of reported study-related adverse events during the treatment period using a t-test or nonparametric test, depending on the distribution. In addition, we will conduct an exploratory analysis using logistic regression to examine the interaction between the treatment arms (NRT versus no NRT by continue EC versus quit EC) with CO-verified 7-day point-prevalence abstinence as the outcome. We will also examine the effect of EC continuation versus NRT on CC abstinence by comparing Group B (quit CCs and Ecs with NRT) versus Group C (quit CCs and continue Ecs without NRT) using logistic regression. We will conduct a series of sensitivity analyses using 30-day abstinence at the 6-month follow up as the outcome and test condition as a predictor of time to relapse after quit day using Cox proportional hazards regression survival analyses. Finally, we will conduct sensitivity analyses when missing data are treated as missing.

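### Removing persistent smokers with raised e-cigarette use from the study, mainly in the continue-EC arms, fixes them as smoking and tilts Aim 2 against continuing ECs by an unknown, probably small amount

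*Combined protocol and SAP*

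**What the plan says.** The adverse-event paragraph under Assessments anticipates raised vaping on one side of the Aim 2 factor: "It is possible that some participants in conditions A and C will increase their EC use when quitting CCs". An increase in people who have fully quit cigarettes is not an adverse event. In people who continue to smoke, an increase above 100% is one. Staff call a participant who continues to smoke and "reports an increase in EC use from baseline of >100% for one week" or longer, and encourage them to cut down ECs or quit cigarettes. The last step is removal: those who continue to smoke and "use > 100% of baseline ECs for two consecutive weeks will be referred to the national quitline and removed from this study".

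The Treatment section gives the two sides opposite instructions. The plan will "instruct participants in groups A and C to use ECs in place of CCs to help cope with cravings", and for the other side: "We will instruct participants in groups B and D to abstain from vaping because ECs could trigger relapse to CCs".

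Under Statistical methods, "our primary analysis will include all randomized participants who complete the baseline survey, independent of early dropout". The rule for missing outcomes is: "Participants who are missing abstinence data will be assumed to be smoking". One alternative is planned: "we will conduct sensitivity analyses when missing data are treated as missing".

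The Withdrawal Procedures section covers harm, invalid data and voluntary withdrawal. It does not say whether a withdrawn or removed participant is still followed for the outcome.

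**The concern.** The rule takes people out of the study, not only off treatment. With no described follow-up afterwards, the plain reading is that the month-3 survey and CO test are not done. The plan's own rule then creates missing outcomes, mostly on one side of a primary comparison, among people who were told to use ECs in place of cigarettes.

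Scoring a removed participant as smoking is correct only if that person is still smoking at month 3. The outcome is 7-day point-prevalence abstinence at the end of treatment, so a later quit would count. The daily surveys run for one week either side of the quit date and fall in weeks 2 and 3, which puts the quit date at about the end of week 2. If vaping rises at that point, removal comes at about the end of week 4, and 12 − 4 = 8 weeks of the treatment period remain. The participant entered wanting to quit and has just been referred to a quitline.

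The bias runs against Hypothesis 2, so it cannot produce a false success for it. It could hide a benefit of continuing ECs or favour quitting both products. The section on dissemination and future directions says that a benefit of quitting both would shape the follow-on research.

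**Working it through.** **Inputs from the documents.** Sample size justification: 78 per group, so 2 × 78 = 156 per factor level; assumed abstinence 28% (cigarettes only, i.e. continue EC) vs 15% (quit both); α = .05; stated Aim 2 power 80%; 390 randomized, 312 expected to be retained. Sidedness is not stated; two-sided is assumed.

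**Reproducing the stated power.** Pooled two-proportion test with n per level and mean rate p̄:

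z = [(p₁ − p₂)√n − 1.96·√(2p̄(1 − p̄))] / √(p₁(1 − p₁) + p₂(1 − p₂))

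With p₁ = .28, p₂ = .15, p̄ = .215, n = 156: z = (1.624 − 1.96 × 0.581) / 0.574 = 0.845, so power is 80.1%. This matches the stated 80%.

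**Bias model.** Let r be the excess share removed in A and C, and q the share of those removed who would have answered the month-3 survey and been CO-verified abstinent. Each such person is scored as smoking, so the continue-EC rate falls from .28 to .28 − r·q and the Aim 2 difference falls by r·q. A removed quitter who would have skipped the survey or the CO test is scored as smoking either way and adds nothing to q.

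**Results.** r and q are assumptions; the documents give neither.

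| r | q | Shift (points) | Continue-EC rate | Difference (points) | Power, n = 156 |
|---|---|---|---|---|---|
| any | 0 | 0 | 28.0% | 13.0 | 80.1% |
| 2% | 5% | 0.1 | 27.9% | 12.9 | 79.6% |
| 5% | 5% | 0.25 | 27.75% | 12.75 | 78.7% |
| 5% | 10% | 0.5 | 27.5% | 12.5 | 77.3% |
| 10% | 10% | 1.0 | 27.0% | 12.0 | 74.2% |
| 10% | 15% (upper end) | 1.5 | 26.5% | 11.5 | 70.9% |

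The number of verified quitters lost on the continue-EC side is 156·r·q: 0.2 at (2%, 5%), 0.8 at (5%, 10%) and 2.3 at (10%, 15%).

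**If B and D also lose some.** The rule covers every arm. If B and D are removed at a quarter of the A and C rate, with the same q, the shift shrinks by a quarter: at 10% removed in A and C and q = 10%, it is 0.75 point instead of 1.0.

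**Dependence on the power base.** The primary analysis set is up to 390/2 = 195 per level. If 28% and 15% hold unchanged there, power is 88.1% without removal and 80.2% at (10%, 15%). If those rates describe only the 80% retained and the rest count as smoking, they become .8 × 28 = 22.4% and .8 × 15 = 12%, and power is 77.9% before any removal. The shift r·q does not depend on this choice.

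**The planned alternative analysis.** Treating missing as missing drops those removed from the denominator, so the continue-EC rate becomes (.28 − r·q)/(1 − r). At r = 10%, q = 10%, with no other missing data, this is .27/.90 = 30%: a difference of 15 points against a true 13. It errs in the other direction because it discards likely smokers, mainly from A and C.

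**The case against.** The strongest reply is that the rule selects people unlikely to be abstinent at month 3. Anyone who has fully quit cigarettes is exempt however much they vape. Staff call after one week and encourage change, and removal follows only if smoking and raised vaping last two weeks. Scoring such a person as smoking carries forward a status just observed. CO samples are voluntary and 20% attrition is planned, so some later quitters would have been scored as smoking anyway. r may also be limited: entry requires vaping on at least 10 of the past 30 days, so if use is counted in days, nobody above 15 of 30 can more than double. The paragraph does not define the unit. All of this stands, and it is why the low rows of the table are more plausible than the high ones. It does not make q zero.

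A second reply is that persistent smoking with doubled vaping may fairly be called treatment failure. That is defensible as a definition, but the plan does not adopt it, and the intent-to-treat approach that it cites favours follow-up.

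A reader might infer three stronger things that the documents do not support:

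- **Aim 2 is seriously compromised.** No figure for r or q supports that.
- **Anyone vaping above baseline is removed.** The removal sentence can be read literally that way, which would make r much larger. However, the adverse-event definition and the call in the same paragraph use an increase above 100%, so the removal wording is probably shorthand for the same level.
- **The primary and missing-as-missing analyses bracket the true effect.** They err in opposite directions when removal is the only missingness, but bracketing is not shown once the planned 20% attrition is added.

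**Conclusion.** The mechanism follows from the plan as written: removal from the study, no described outcome collection afterwards, scoring as smoking, and a trigger tied to the Aim 2 factor. The shift is r × q against continuing ECs. It is zero if nobody removed would have been verified abstinent, and probably small otherwise. Over the assumed range it is 0.1 to 1.5 of the planned 13 points, taking power from 80.1% to between 79.6% and 70.9% on the plan's own base. The conclusion rests on three assumptions: removed participants are not followed, removals fall mainly in A and C, and r and q lie in the ranges shown. The planned alternative analysis does not correct the shift. This is a cheap improvement to consider, not a defect that invalidates the comparison.

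**What to change.** In the adverse-event paragraph under Assessments, replace removal from the study with stopping study treatment plus the quitline referral. Keep these participants in the already planned 3- and 6-month surveys and CO tests. Score them on observed status, and as smoking only if they then do not respond. Say the same under Withdrawal Procedures.

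As a separate, minor wording point, use one threshold, an increase of more than 100% from baseline, for both the call and stopping treatment. The investigators should confirm that a smoker vaping at one to two times baseline may stay on treatment.

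The cost is a short amendment and a few contacts that are already scheduled. Participants keep their CO device, no sample size is added, and the safety purpose is preserved because study treatment still ends.
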